Marrow CR	
Bone marrow: $\leq 5\%$ myeloblasts and decrease by $\geq 50\%$ over pretreatment
 
Peripheral blood: if HI responses, they will be noted in addition to marrow CR

Stable disease	Failure to achieve at least PR, but no evidence of progression for > 8 wks
Failure	Death during treatment or disease progression characterized by worsening of cytopenias, increase in percentage of bone marrow blasts, or progression to a more advanced MDS FAB subtype than pretreatment
Relapse after CR or PR	
At least 1 of the following:
 
 • Return to pretreatment bone marrow blast percentage • Decrement of $\geq 50\%$ from maximum remission/response levels in granulocytes or platelets • Reduction in Hgb concentration by ≥ 1.5 g/dL or transfusion dependence
Cytogenetic response	
Complete - Disappearance of the chromosomal abnormality without appearance of new ones
 
Partial - At least 50% reduction of the chromosomal abnormality

Disease progression	
For patients with:
 
 • Less than 5% blasts: $\geq 50\%$ increase in blasts to $> 5\%$ blasts • 5%-10% blasts: $\geq 50\%$ increase to $> 10\%$ blasts • 10%-20% blasts: $\geq 50\%$ increase to $> 20\%$ blasts • 20%-30% blasts: $\geq 50\%$ increase to $> 30\%$ blasts 
Any of the following:
 
 • At least 50% decrement from maximum remission/response in granulocytes or platelets • Reduction in Hgb by > 2 g/dL • Transfusion dependence
*Dysplastic changes should consider the normal range of dysplastic changes (modification).	
¹ Cheson, et al. Clinical application and proposal for modification of the International Working Group (IWG) response criteria in myelodysplasia. blood-2005-10-4149.	

14.13 Appendix M: Myeloproliferative Neoplasm (MPN) Symptom Assessment Form Total Symptom Score (MPN-SAF-TSS)

Name: _____ Date: _____

Fill out the form below to track the burden of your symptoms.

For each symptom, please **circle the number** that best describes how severe that symptom is, on a scale of 0 to 10, with **0 being absent or as good as it can be** and **10 being worst imaginable**. Make sure you circle a number for every symptom. Be sure to **share your answers** with your hematologist or other healthcare professional.

Symptom - 1 to 10, 0 if absent and 10 being worst imaginable

Please rate your fatigue (weariness, tiredness) by circling the one number that best describes your **WORST** level of fatigue during the **past 24 hours**

Fatigue

0	1	2	3	4	5	6	7	8	9	10
---	---	---	---	---	---	---	---	---	---	----

(ABSENT) (WORST IMAGINABLE)

Circle the one number that describes how much difficulty you have had with each of the following symptoms during the **past week**

Filling up quickly when you eat (early satiety)

0	1	2	3	4	5	6	7	8	9	10
---	---	---	---	---	---	---	---	---	---	----

(ABSENT) (WORST IMAGINABLE)

Abdominal discomfort

0	1	2	3	4	5	6	7	8	9	10
---	---	---	---	---	---	---	---	---	---	----

(ABSENT) (WORST IMAGINABLE)

Inactivity

0	1	2	3	4	5	6	7	8	9	10
---	---	---	---	---	---	---	---	---	---	----

(ABSENT) (WORST IMAGINABLE)

Problems with concentration - compared to before my diagnosis

0	1	2	3	4	5	6	7	8	9	10
---	---	---	---	---	---	---	---	---	---	----

(ABSENT) (WORST IMAGINABLE)

Night sweats

[figure not shown]
0	1	2	3	4	5	6	7	8	9	10
---	---	---	---	---	---	---	---	---	---	----

(ABSENT) (WORST IMAGINABLE)

Itching (pruritus)

0	1	2	3	4	5	6	7	8	9	10
---	---	---	---	---	---	---	---	---	---	----

(ABSENT) (WORST IMAGINABLE)

Bone pain (diffuse, not joint pain or arthritis)										
0	1	2	3	4	5	6	7	8	9	10
(ABSENT)						(WORST IMAGINABLE)				
Fever (> 37.8°C or 100°F)										
0	1	2	3	4	5	6	7	8	9	10
(ABSENT)						(WORST IMAGINABLE)				
Unintentional weight loss last 6 months										
0	1	2	3	4	5	6	7	8	9	10
(ABSENT)						(WORST IMAGINABLE)				

To help you get a clear overall picture of how you are feeling, you can add up all your scores to calculate your Total Symptom Score.

Total

¹ Adapted from Emanuel RM, Dueck AC, Geyer HL, et al. Myeloproliferative neoplasm (MPN) symptom assessment form total symptom score: prospective international assessment of an abbreviated symptom burden scoring system among patients with MPNs [published correction appears in J Clin Oncol. 2012;30(36):4590]. J Clin Oncol. 2012;30(33):4098-4103

14.14 Appendix N: Eastern Cooperative Oncology Group (ECOG) performance status

Score	Performance status
0	Fully active, able to carry on all pre-disease performance without restriction.
1	Restricted in physically strenuous activity but ambulatory and able to carry out work of a light or sedentary nature, e.g. light housework, office work.
2	Ambulatory and capable of all self-care but unable to carry out any work activities. Up and about more than 50% of waking hours.
3	Capable of only limited self-care, confined to bed or chair more than 50% of waking hours.
4	Completely disabled. Cannot carry on any self-care. Totally confined to bed or chair.
5	Dead

14.15 Appendix O: International Myeloma Working Group (IMWG) uniform response criteria for multiple myeloma

Response	IMWG Criteria
sCR	CR as defined below plus normal FLC ratio and absence of clonal cells in bone marrow ³ by immunohistochemistry or immunofluorescence ⁴
CR	Negative immunofixation on the serum and urine and disappearance of any soft tissue plasmacytomas and < 5% plasma cells in bone marrow ³
VGPR	Serum and urine M-component detectable by immunofixation but not on electrophoresis or ≥ 90% reduction in serum M-component plus urine M-component < 100 mg per 24 hr
PR	> 50% reduction of serum M-protein and reduction in 24 hours urinary M-protein by >90% or to < 200 mg/24 h If the serum and urine M-protein are unmeasurable, ⁵ a > 50% decrease in the difference between involved and uninvolved FLC levels is required in place of the M-protein criteria If serum and urine M-protein are not measurable, and serum free light assay is also not measureable, > 50% reduction in plasma cells is required in place of M-protein, provided baseline bone marrow plasma cell percentage was > 30% In addition to the above listed criteria, if present at baseline, a > 50% reduction in the size of soft tissue plasmacytomas is also required
SD	Not meeting criteria for CR, VGPR, PR, or progressive disease
PD ⁵	Increase of > 25% from lowest response value in any one or more of the following: Serum M-component and/or (the absolute increase must be > 0.5 g/dL) ⁶ Urine M-component and/or (the absolute increase must be > 200 mg/24 h) Only in patients without measurable serum and urine M-protein levels; the difference between involved and uninvolved FLC levels. The absolute increase must be > 10 mg/dL Bone marrow plasma cell percentage; the absolute percentage must be > 10% ⁷ Definite development of new bone lesions or soft tissue plasmacytomas or definite increase in the size of existing bone lesions or soft tissue plasmacytomas Development of hypercalcemia (corrected serum calcium > 11.5 mg/dL or 2.65 mmol/L) that can be attributed solely to the plasma cell proliferative disorder
Relapse	Clinical relapse requires one or more of: Direct indicators of increasing disease and/or end organ dysfunction (CRAB features). ⁶ It is not used in calculation of time to progression or progression-free survival but is listed here as something that can be reported optionally or for use in clinical practice Development of new soft tissue plasmacytomas or bone lesions Definite increase in the size of existing plasmacytomas or bone lesions. A definite increase is defined as a 50% (and at least 1 cm) increase as measured serially by the sum of the products of the cross-diameters of the measurable lesion Hypercalcemia (> 11.5 mg/dL) [2.65 mmol/L] Decrease in haemoglobin of > 2 g/dL [1.25 mmol/L] Rise in serum creatinine by 2 mg/dL or more [177 mmol/L or more]

¹ BGM Durie et al. International uniform response criteria for multiple myeloma. Leukemia (2006) 1-7.

² Adapted from Durie BGM, et al. Leukemia 2006; 20: 1467-1473; and Kyle RA, Rajkumar SV. Leukemia 2008;23:3-9

Response IMWG Criteria

Note: A clarification to IMWG criteria for coding CR and VGPR in patients in whom the only measurable disease is by serum FLC levels: CR in such patients is defined as a normal FLC ratio of 0.26–1.65 in addition to CR criteria listed above. VGPR in such patients is defined as a >90% decrease in the difference between involved and unininvolved free light chain (FLC) levels.

3. Confirmation with repeat bone marrow biopsy not needed.
4. Presence/absence of clonal cells is based upon the kappa/lambda ratio. An abnormal kappa/lambda ratio by immunohistochemistry and/or immunofluorescence requires a minimum of 100 plasma cells for analysis. An abnormal ratio reflecting presence of an abnormal clone is kappa/lambda of > 4:1 or < 1:2.
5. All relapse categories require two consecutive assessments made at any time before classification as relapse or disease progression and/or the institution of any new therapy. In the IMWG criteria, CR patients must also meet the criteria for progressive disease shown here to be classified as progressive disease for the purposes of calculating time to progression and progression-free survival. The definitions of relapse, clinical relapse and relapse from CR are not to be used in calculation of time to progression or progression-free survival.
6. For progressive disease, serum M-component increases of >1 gm/dL are sufficient to define relapse if starting M-component is >5 g/dL.
7. Relapse from CR has the 5% cut-off versus 10% for other categories of relapse.
8. For purposes of calculating time to progression and progression-free survival, CR patients should also be evaluated using criteria listed above for progressive disease.

14.16 Appendix P: List of concomitant medications

In general, the use of any concomitant medication deemed necessary for the care of the patient is permitted in this study, except as specifically prohibited below. Combination administration of study drugs could result in drug-drug interactions (DDI) that could potentially lead to reduced activity or enhanced toxicity of the concomitant medication and/or BGJ398.

The following lists are based on the Oncology Clinical Pharmacology Drug-Drug Interaction Database (release date: 29 Oct 2012), which was compiled from the Indiana University School of Medicine's "Clinically Relevant" Table and supplemented with the FDA Draft guidance.

14.16.1 Drugs to be used with caution while on study

Category	Drug Names
Sensitive CYP3A Substrates	Alpha-dihydroergocryptine, aplaviroc, aprepitant, atorvastatin, brecanavir, brotizolam, budesonide, buspirone, capravirine, casopitant, conivaptan, darifenacin, darunavir, dasatinib, dronedarone, ebastine, eletriptan, eplerenone, everolimus, felodipine, fluticasone, indinavir, levomethadyl, lopinavir, lovastatin, lumefantrine, lurasidone, maraviroc, midazolam, neratinib, nisoldipine, perospirone, quetiapine, ridaforolimus, saquinavir, sildenafil, simvastatin, ticagrelor, tipranavir, tolvaptan, triazolam, vardenafil, vicriviroc
Moderate inhibitors of CYP3A4	Amprenavir, aprepitant, atazanavir, casopitant, cimetidine, ciprofloxacin, cyclosporine, darunavir, diltiazem, dronedarone, erythromycin, fluconazole, fosamprenavir, imatinib, Schisandra sphenanthera, tofisopam, verapamil
Moderate inducers of CYP3A4	Bosentan, efavirenz, etravirine, genistein, modafinil, naftcilin, ritonavir, talviraline, thioridazine, tipranavir
Medications which alter the pH of the GI tract ¹	Proton-pump inhibitors (e.g., omeprazole), H2-antagonists (e.g., ranitidine) and antacids.
Medications that have possible risk of TdP/QT prolongation	Dronedarone, eribulin, lapatinib, sunitinib, nilotinib, tamoxifen, gatifloxacin, gemifloxacin, levofloxacin, ofloxacin, roxithromycin, telithromycin, clozapine, iloperidone, paliperidone, quetiapine, risperidone, sertindole, ziprasidone, dolasetron, granisetron, ondansetron, escitalopram, venlafaxine, Ranolazine, voriconazole, amantadine, foscarnet, isradipine, moexipril, nicardipine, fingolimod, tacrolimus, atazanavir, felbamate, famotidine, fosphenytoin, alfuzosin, chloral hydrate, indapamide, lithium, octreotide, pasireotide, oxytocin, ranolazine, tizanidine, vardenafil

Category	Drug Names
Medications that have conditional risk of TdP/QT prolongation	Amisulpride, amitriptyline, clomipramine, desipramine, doxepin, fluoxetine, imipramine, nortriptyline, paroxetine, protriptyline, sertraline, trazodone, trimipramine, ciprofloxacin, trimethoprim-sulfa, diphenhydramine, fluconazole, itraconazole, ketoconazole, ritonavir, galantamine, solifenacin
BCRP substrates	Rosuvastatin, methotrexate, irinotecan, atorvastatin, simvastatin, topotecan, sulfasalazine

¹ BGJ398 should be dosed at least 2 hours before or 10 hours after dosing with a gastric protection agent.

Reference:

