6.4.2.4 Anti-emetics

Anti-emetics are allowed for the treatment of nausea or vomiting. It is recommended to avoid using drugs that are known to cause QT prolongation. Note that some anti-emetics have a known risk for Torsade de Pointes, and therefore need to be used with caution ([Appendix C](#)). Aprepitant is both a sensitive substrate and a moderate CYP3A4 inhibitor and should be used with caution if an alternative is not available.

6.4.2.5 Medications with a possible or conditional risk of QT/QTc interval prolongation or Torsade de Pointes

Preliminary data have shown that BGJ398 has no effect on cardiac conduction or ECG intervals (see current version of the BGJ398 Investigator Brochure). However, medications that have the potential to prolong the QT/QTc interval or induce Torsade de Pointes are allowed with caution. Investigators at their discretion may co-administer such medications, but patients should be carefully monitored. See [Appendix P](#) for list of drugs that need to be used with caution. Please note that the list might not be comprehensive.

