6.4.3.5 Known risk of QT/QTc interval prolongation or Torsade de Pointes medications

Preliminary data have shown that BGJ398 has no effect on cardiac conduction or ECG intervals (See current version of the BGJ398 [Investigator's Brochure]). However, medications that are known to prolong the QT/QTc interval or induce Torsade de Pointes (Risk of TdP/QT prolongation) are prohibited.

Please refer to [Appendix Q](#) for the list of prohibited medications. Please note that the list might not be comprehensive.

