14.3 Appendix C: Ann Arbor staging classification

Not applicable. Please refer to BGJ398XUS04 Protocol Version 02

Stage	Area of involvement
I	Single lymph node group
II	Multiple lymph node groups on the same side of the diaphragm
III	Multiple lymph node groups on both sides of the diaphragm
IV	Multiple extranodal sites or lymph nodes and extranodal disease
X	Bulk disease > 10 cm
E	Extranodal extension or single isolated site of extranodal disease
Class A are patients who experience no B symptoms	
Class B are patients experience unexplained fever of $\geq 38^{\circ}\text{C}$; unexplained, recurrent drenching night sweats; or unexplained loss of >10% body weight within the previous 6 months	

¹ Cotswolds modification of Ann Arbor staging system adapted from 2007 NCCI guidelines for non-Hodgkin's lymphoma

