14.17 Appendix Q: List of prohibited medication

14.17.1 List of prohibited medication while on study

Category	Drug Names
Strong inducers of CYP3A4	Avasimibe, carbamazepine, phenobarbital, phenytoin, rifabutin, rifampin, St. John's wort
Strong Inhibitors of CYP3A4	Clarithromycin, conivaptan, indinavir, itraconazole, ketoconazole, voriconazole, lopinavir, mibefradil, nefazodone, neflifavir, posaconazole, ritonavir, saquinavir, telithromycin, grapefruit juice, juice from Seville oranges
Medications which increase serum phosphorus and/or calcium	Calcium, phosphate, vitamin D, parathyroid hormone (PTH)
Narrow Therapeutic index substrates of CYP3A4	Quinidine, astemizole, terfanadine, cyclosporine, sirolimus, tacrolimus, diergotamine, cisapride, ergotamine, pimozide, alfentanil, fentanyl, thioridazine, diergotamine, dihydroergotamine, ergotamine
Medications with established potential for QT prolongation or Torsades de pointes	Amiodarone, Anagrelide, Arsenic trioxide, Astemizole (Off US mkt), Azithromycin, Bepridil (Off US mkt), Chloroquine, Chlorpromazine, Cisapride (Off US mkt), Citalopram, Clarithromycin, Cocaine, Disopyramide, Dofetilide, Domperidone (Not on US mkt), Dronedarone, Droperidol, Erythromycin, Escitalopram, Flecainide, Grepafloxacin (Off market worldwide), Halofantrine, Haloperidol, Ibutilide, Levofloxacin, Levomethadyl (Off US mkt), Mesoridazine (Off US mkt), Methadone, Moxifloxacin, Ondansetron, Pentamidine, Pimozide, Probucon (Off US mkt), Procainamide (Oral off US mkt), Quinidine, Sevoflurane, Sotalol, Sparfloxacin (Off US mkt), Sulpiride (Not on US Mkt), Terfenadine (Off US mkt), Thioridazine, Vandetanib

14.18 Appendix R: Bayesian Adaptive Design Framework for the Modular phase II study to link targeted therapy to patients with pathway activated tumors

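### Four QT drugs are caution drugs in Appendix P and prohibited in Appendix Q; the anti-emetic rule and the TIO supplement rule conflict similarly (minor safety-wording correction)

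*Protocol*

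**What the plan says.** **QT drugs.** Section 6.4.2.5 covers drugs with a possible or conditional QT risk. It says that "Investigators at their discretion may co-administer such medications", with monitoring, and refers to Appendix P for the list. The possible-risk row there contains "ondansetron, escitalopram" as well as dronedarone and levofloxacin. The established-potential row of Appendix Q contains all four: "Dronedarone, Droperidol, Erythromycin, Escitalopram, Flecainide", "Ibutilide, Levofloxacin, Levomethadyl" and "Moxifloxacin, Ondansetron, Pentamidine".

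**Anti-emetics.** Section 6.4.2.4 first recommends avoiding drugs known to prolong QT. It then notes that "some anti-emetics have a known risk for Torsade de Pointes, and therefore need to be used with caution" and cites Appendix C. That appendix is "Appendix C: Ann Arbor staging classification". Section 6.4.3.5 says that "medications that are known to prolong the QT/QTc interval or induce Torsade de Pointes (Risk of TdP/QT prolongation) are prohibited".

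**TIO supplements.** For ongoing TIO patients, 6.4.1 allows phosphate, titrated as needed during BGJ398 treatment, and also calcitriol and cinacalcet. Section 6.4.3.4 prohibits medications that raise serum phosphorus or calcium. Appendix Q names phosphate and vitamin D in that class. Neither mentions TIO.

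**Precedence and consequence.** Section 6.4 makes the permissions in 6.4.1 and 6.4.2 subject to the prohibitions in 6.4.3, and the introduction to Appendix P has a similar proviso. Section 7.1.3.2 puts use of prohibited medication, with a reference to 6.4.3, among the study-specific criteria that require stopping study treatment.

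**The concern.** These are operative safety rules. An investigator choosing an anti-emetic or an antibiotic will go to the section on that subject and to the list it cites. Neither 6.4.2.4 nor 6.4.2.5 leads to Appendix Q. A site following either could give ondansetron or levofloxacin as a caution drug and meet a criterion for stopping study treatment. Anti-emetic use is plausible: section 1.2.1.2.1 reports nausea in 31.4% and vomiting in 20.8% of the 207 phase I patients.

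For TIO the problem runs the other way. The supplements that the protocol means to allow fall inside a prohibition with no stated exception.

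What is at stake is consistent, safe conduct at sites. No estimate or operating characteristic depends on it.

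**Working it through.** There is no plan figure to reproduce. The check has two parts: a comparison of the drug lists, and a reading of the rules side by side.

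**1. Drug lists.** Inputs: every name in Appendix P (14.16.1) and Appendix Q (14.17.1), by category, matched on exact name without regard to case.

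| Quantity | Result |
|---|---|
| Names in both appendices | 18 |
| Of these, in a QT row of P and the QT row of Q | 4 (dronedarone, escitalopram, levofloxacin, ondansetron) |
| Overlap by a different mechanism | 18 − 4 = 14 |
| Appendix P entries for the four | 3 + 1 + 1 + 1 = 6 (dronedarone is in three rows) |
| Appendix P entries for the 14 | 2 + 13 = 15 (ritonavir is in two rows) |
| Total Appendix P entries | 6 + 15 = 21 |

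The 14 are:
- Sensitive CYP3A substrate in P, strong inhibitor in Q: conivaptan, indinavir, lopinavir, saquinavir.
- Conditional QT in P, strong inhibitor in Q: itraconazole, ketoconazole.
- Possible QT in P, strong inhibitor in Q: telithromycin, voriconazole.
- Moderate inducer and conditional QT in P, strong inhibitor in Q: ritonavir.
- Moderate inhibitor in P, narrow therapeutic index in Q: cyclosporine.
- Possible QT in P, narrow therapeutic index in Q: tacrolimus.
- Moderate inhibitor in P, QT in Q: erythromycin.
- Sensitive substrate in P, QT in Q: levomethadyl.
- Moderate inducer in P, narrow therapeutic index and QT in Q: thioridazine.

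The possible-risk row of P has 46 distinct names. Removing the four leaves 46 − 4 = 42. Removing telithromycin, voriconazole and tacrolimus as well leaves 42 − 3 = 39. The conditional-risk row has 22; removing itraconazole, ketoconazole and ritonavir leaves 22 − 3 = 19. The caution lists therefore stay useful after the correction.

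**2. Rules side by side.**

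| Subject | Permits or cautions | Prohibits | Which governs |
|---|---|---|---|
| Four QT drugs | 6.4.2.5 and Appendix P | 6.4.3.5 and Appendix Q | Prohibition, by 6.4 |
| Known-risk anti-emetics | 6.4.2.4, citing Appendix C in error | 6.4.3.5 | Prohibition, by 6.4 |
| Phosphate and calcitriol, ongoing TIO | 6.4.1 | 6.4.3.4 and Appendix Q | Prohibition on the letter of 6.4; permission on evident intent |

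Calcitriol falls under the vitamin D entry because section 2.1 itself describes it as activated vitamin D. For TIO the intent is plain from three places. Exclusion 7 exempts TIO from the same restriction at entry. Section 6.4.1.3 withholds prophylactic phosphate-lowering therapy in TIO. The TIO criterion in 10.4 requires freedom from supplementation only for at least the cycle before the 16-week assessment, which presupposes that supplements may be used earlier.

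**The case against.** The strongest reply is that the protocol already settles most of this. Section 6.4 subordinates permissions to prohibitions, so no QT drug is left without a governing rule. That stands, and it disposes of the 14 different-mechanism overlaps as contradictions: a drug can be a CYP3A substrate and also a prohibited strong inhibitor. It does not excuse giving four drugs two different QT grades, because an investigator sent only to Appendix P does not see the second grade.

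For anti-emetics, 6.4.2.4 does open by advising against QT-prolonging drugs. What remains is the gap between advice to avoid and prohibition, plus a wrong appendix letter.

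For TIO, a reader might infer that the protocol forces ongoing patients off BGJ398 for taking supplements it allows. That follows only if 6.4.3.4, Appendix Q and 7.1.3.2 are read literally and the specific permission in 6.4.1 is ignored. The documents point clearly to the opposite intent, and sites would probably follow 6.4.1.

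A reader might also infer that inclusion 14a, which allows supplementation to reach eligible laboratory values, contradicts exclusion 7. The text does not support that. Exclusion 7 concerns use of such medications, eligibility is re-checked on C1D1 under 6.1.1, and 6.4.3.4 bars these drugs on study. Correcting the values in screening and stopping before C1D1 satisfies both criteria. Exclusions 11 and 12 give no day count either, so the missing window is absent detail, not a conflict.

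**Conclusion.** The wording conflicts are real and worth correcting, but minor. Four drugs have inconsistent QT grades across the caution and prohibited lists. One anti-emetic rule is softer than the prohibition that governs it and cites a staging table. One TIO exception was not carried into 6.4.3.4 or Appendix Q.

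The count of 18 shared names should not be read as 18 contradictions; only the four are graded differently for the same risk. The number of patients affected is unknown and may be zero for TIO. Amendment 3 enrolls no new TIO patients. Section 4.1.1 has TIO patients without metabolic benefit by week 16 stop unless the sponsor approves otherwise. SAP section 2 says most subjects have already discontinued. Preliminary data in section 1.2.1.2.1 show no QT effect of BGJ398, which also limits the safety consequence.

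The conclusion assumes only that investigators use the section and appendix they are sent to. It implies no effect on clinical benefit rate, error rates or power.

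**What to change.** 1. Delete dronedarone, escitalopram, levofloxacin and ondansetron from the possible-risk QT row of Appendix P. For clarity, delete the other shared names too, and dronedarone from its two other rows (21 entries in all). State that Appendix Q prevails over Appendix P. The statement is useful because cyclosporine and tacrolimus are prohibited only through the narrow-therapeutic-index row of Appendix Q, which no subsection of 6.4.3 covers.
2. In 6.4.2.4, state that any anti-emetic listed in Appendix Q is prohibited, and cite Appendices P and Q in place of Appendix C.
3. In 6.4.3.4 and Appendix Q, add an exception for phosphate and calcitriol in ongoing TIO patients, matching the note in exclusion 7.

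The cost is a wording amendment. Design, eligibility, sample size and analysis do not change.
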